8.3.3 Intent-to-Treat (ITT) Population

Not applicable.

8.3.4 Per Protocol (PP) Population

Not applicable.

8.3.5 Pharmacokinetics (PK) population

The PK analysis set will consist of all subjects in the Efficacy Analysis Set who have received at least one dose of AZD5718, and who have at least one PK sample post dose.

A patient will be considered as having at least one PK sample post dose if he has at least one plasma concentration that is not below LoQ after the first dose.

Subjects will be analysed according to the treatment which they actually received. However, only samples taken on patients planned to receive AZD5718 are analysed. Thus, patients planned to receive placebo but who finally received AZD5718 will not have any result available.

8.4 Demographic and Other Baseline Characteristics

All demographics and baseline characteristics will be presented by treatment group and overall. They will be based on the Efficacy Analysis Set. Demographic and other baseline characteristics are described in section 6.3.

Demographic characteristics and Subject characteristics

Demographic characteristics will be presented by cohort of patients and will include Age (years), Age group (<50; >=50 -<65; >=65 years), sex, race, ethnicity and country. Subject characteristics will include height (cm), weight (kg), weight group (<70; >=70- <=90; >90 kg), BMI ((kg/m2) and BMI group (Normal <25; Overweight >=25-<=30; Obese >30 kg/m2). All these variables will be summarized as described in section 7.1.

Age, sex, race, weight, height and BMI will also be listed for all randomized subjects.

Distribution:

Original:

Copy:

TPCA025 Version 2 (based on TPQA036 Version 2) Effective Date: 27th August 2017 Prior Effective Date: 21st December 2016

Sponsor:	AstraZeneca AB	Protocol/CIP Number:	D7550C00003
CIL Project Number:	40343		

Nicotine and alcohol usage

Nicotine use and alcohol use and consumption will be summarized with descriptive statistics. Alcohol use will be also listed for all randomized subjects.

Medical history

Relevant medical and surgical history and Specific medical and surgical history will be coded in MedDRA 20.0 or higher and will be summarized by System Organ Class (SOC) and Preferred Term (PT). The number and percentage of subjects with any Relevant and Specific medical and surgical history will be summarized by SOC and PT.

8.5 Prior and Concomitant Medications

The WHO-DDE + HD Drug Dictionary version 2017Jun B3 or higher will be used to classify medications by WHO Anatomical Therapeutic Chemical (ATC) classification of ingredients.

Medication will be classified as either prior or concomitant (but not both) according to its stop date. Prior medication is defined as any medication with a stop date prior to the first dose of study drug (exclusive).

Concomitant medication is defined as any medication with a start date on or before the last dose of study drug and a stop date on or after the first dose of study drug, or any medication taken prior to last dose of study drug and that is ongoing.

It is of note that classification is not based on eCRF question "Taken prior to study?" but derived according to the medication stop date rule as above.

The imputation method described in section 7.3 will be used in case of medication stop date partially missing. Completely missing start or stop dates will not be replaced, and medication will be classified as concomitant.

The number and percentage of subjects with at least one allowed concomitant medication and the number and percentage of subjects by ATC codes will be provided using the Efficacy Analysis Set. An exhaustive list of disallowed medications (coding and indication wherever applicable) is reported in the Integrated Data Review Plan (IDRP), "Prohibited Medication" tab. Prohibited Medications taken during the study, will be confirmed and flagged by AZ study physician in accordance with CSP v3 section 7.7.

The number and percentage of subjects with any allowed concomitant medication will also be summarized by ATC level 4 (therapeutic subgroup) and product name.

A listing of previous and concomitant medications with ATC codes will be provided for all randomized subjects. Duration (day) will be calculated as stop date minus start date +1. If start date or stop date is partially or completely missing duration will be missing.

Distribution:

Original:

Copy:

TPCA025 Version 2 (based on TPQA036 Version 2) Effective Date: 27th August 2017 Prior Effective Date: 21st December 2016

Sponsor:	AstraZeneca AB	Protocol/CIP Number:	D7550C00003
CIL Project Number:	40343		

8.6 Analysis of Efficacy Parameters

Efficacy parameters include:

- Creatinine-normalised u-LTE₄
- CFVR
- LAD resting mean diastolic flow velocity
- LAD hyperaemic flow velocity
- LV ejection fraction (LVEF) at rest
- LV Global Longitudinal Strain (GLS) at rest and at hyperaemia
- LV Global Circumferential Strain (GCS) at rest
- LV longitudinal early diastolic strain rate

Efficacy endpoints of the study are:

Primary endpoint:

• percent change in creatinine normalized u-LTE₄ at 4 weeks (Visit 4)

Secondary endpoints:

- percent change in creatinine normalized u-LTE₄ at 12 weeks (Visit 4c)
- change in CFVR at 12 weeks (Visit 4c)
- change in CFVR at 4 weeks (Visit 4)

Other secondary endpoints:

 change in LAD resting mean diastolic flow velocity, LAD hyperaemic flow velocity, LV ejection fraction (LVEF) at rest, LV Global Longitudinal Strain (GLS) at rest and at hyperaemia, LV Global Circumferential Strain (GCS) at rest and LV longitudinal early diastolic strain rate at 4 weeks (Visit 4)

To preserve the overall type1-error at 5% when testing these four endpoints a Hierarchical Procedures will be used. This procedure implies that one will test the four endpoints in a predefined sequence: test of main endpoint, test of first secondary endpoint, test of second secondary endpoint, test of third secondary endpoint. The test procedure will stop as soon as the first none-significant test, one-sided test at a 5% level, occur and all following test will be declared as none-significant.

Detailed description of the statistical analyses for each endpoint is reported in the following sections.

In addition to the analyses described below, an overview table for the primary and secondary efficacy results will be provided.

Distribution:

Original:

Copy:

TPCA025 Version 2 (based on TPQA036 Version 2) Effective Date: 27th August 2017 Prior Effective Date: 21st December 2016

Sponsor:	AstraZeneca AB	Protocol/CIP Number:	D7550C00003
CIL Project Number:	40343		

8.6.1 Analysis of primary efficacy variable

The primary efficacy endpoint is to test the null hypothesis that subjects given AZD5718 have less than 80% inhibition of creatinine-normalized u-LTE₄ at visit 4 compared to placebo.

The first secondary efficacy endpoint is to test the null hypothesis that subjects given AZD5718 have less than 80% inhibition of creatinine-normalized u-LTE₄ at visit 4c compared to placebo.

All the analyses will be performed based on the Efficacy Analysis Set. All the assessments related to the first variable are described in section 6.4.1.

For both the endpoints, the change in creatinine-normalized u-LTE₄ will be analysed using the Mixed Model Repeated Measures (MMRM) described in section 7.1 using data from visit 2, 3, 4 and 4c.

Creatinine-normalized u-LTE₄ is log-Normal distributed. The analysed change from Baseline is calculated as Visit value in log minus the Baseline value in log.

One-sided test will be used to compare the change from baseline observed in the active group, vs the change from baseline observed in the placebo group. Alpha level will be set at 0.05. The reportable results will be those for log-Normal variables.

Comparison of AZD5718 versus placebo will also be assessed within the same model.

For further details on the statistical model please refer to the Appendix 2 and to the table in Appendix 3.

Back-up solution for statistical model:

In case the model will not converge for any reasons, the following back-up solutions will be adopted sequentially:

- The compound symmetry will be used instead of the SP (POW);
- The primary efficacy variable will be analysed using the ANCOVA model described in section 7.1 for log-Normal variables instead of using the MRMM model.

In addition to the results above, the following will also be generated:

- Descriptive statistics by group for all visits, for the actual value and for the change from baseline. Change from baseline is calculated as Visit value minus Baseline value;
- Graphical representations of change from baseline (mean(SD)) over time and by groups;
- Forest plots based on the results of the two models.

Creatinine-normalized u-LTE4 will be also listed for Efficacy Analysis Set at each visit.

TPCA025 Version 2 (based on TPQA036 Version 2) Original:

Copy:

Effective Date: 27th August 2017 Prior Effective Date: 21st December 2016

Sponsor:	AstraZeneca AB	Protocol/CIP Number:	D7550C00003
CIL Project Number:	40343		

A sensitivity analysis may be performed as detailed in section 7.2.

8.6.2 Analysis of secondary efficacy variables

Change from baseline in CFVR

The second secondary efficacy endpoint is the change from baseline in CFVR at Visit 4c.

The null hypothesis of no increase in CFVR in subjects given AZD5718 compared to placebo will be tested.

The third secondary efficacy endpoint is the change from baseline in CFVR at Visit 4.

The null hypothesis of no increase in CFVR in subjects given AZD5718 compared to placebo will be tested.

All the analyses will be performed based on the Efficacy Analysis Set. All the assessments related to the secondary variables are described in section 6.4.2.

Both the second and third secondary endpoints will be analysed using the Mixed Model Repeated Measures (MMRM) described in section 7.1 using data from visit 2, 4 and 4c.

CFVR is log-Normal distributed. The analysed change from Baseline is calculated as Visit value in log minus the Baseline value in log.

One-sided test will be used to compare the change from baseline observed in the active group, vs the change from baseline observed in the placebo group. Alpha level will be set at 0.05. The reportable results will be those for log-Normal variables.

Comparison of AZD5718 versus placebo will also be assessed within the same model.

For further details on the statistical model please refer to the Appendix 2 and to the table in Appendix 3.

In addition to the results above, the following will also be generated:

- Descriptive statistics by group for all visits, for the actual value and for the change from baseline. Change from baseline is calculated as Visit value minus Baseline value;
- Graphical representations of change from baseline (mean(SD)) over time and by groups;
- Forest plots based on the results of the two models.

CFVR will be also listed for Efficacy Analysis Set at each visit.

A sensitivity analysis may be performed as detailed in section 7.2.

Distribution:

Original:

Copy:

TPCA025 Version 2 (based on TPQA036 Version 2) Effective Date: 27th August 2017 Prior Effective Date: 21st December 2016

Sponsor:	AstraZeneca AB	Protocol/CIP Number:	D7550C00003
CIL Project Number:	40343		

Other secondary variables

The other secondary endpoints related to all other secondary variables are the changes from baseline at Visit 4. The exploratory endpoints related to all other secondary variables are the changes from baseline at Visit 4c.

The other secondary variables are:

- LAD resting mean diastolic flow velocity
- LAD hyperaemic flow velocity
- LV ejection fraction (LVEF) at rest
- LV Global Longitudinal Strain (GLS) at rest and at hyperaemia
- LV Global Circumferential Strain (GCS) at rest
- LV longitudinal early diastolic strain rate

All the analyses will be performed based on the Efficacy Analysis Set. All the assessments related to the secondary variables are described in section 6.4.2.

These variables will be firstly tested for Normality (Normality will be evaluated using Q-Q plots). Then the changes at visit 4 (secondary endpoints) and the changes at visit 4c (exploratory endpoints) will be analysed using Mixed Model Repeated Measures (MMRM) described in section 7.1_using data from visit 2, 4 and 4c.

If the distribution appears to be Normal, the analysed change will be the Visit value minus the Baseline value. The reportable results will be those for Normal variables.

If the distribution appears to be log-Normal, the analysed change will be the Visit value in log minus the Baseline value in log. The reportable results will be those for log-Normal variables.

The null hypothesis of no difference in subjects given AZD5718 compared to placebo will be tested.

Two-sided test will be used to compare the change from baseline observed in the active group vs the change from baseline observed in the placebo group. Alpha level will be set at 0.05.

Comparison of AZD5718 versus placebo will also be assessed within the same model.

For further details on the model please refer to Appendix 2 and to the table in Appendix 3.

In addition to the results above, also the following will be generated:

- Descriptive statistics by group for all visits, for the actual value and for the change from baseline. Change from baseline is calculated as Visit value minus Baseline value;
- Graphical representations of change from baseline (mean(SD)) over time and by groups;
- Forest plots based on the results of the models.

Distribution:

Original:

Copy:

TPCA025 Version 2 (based on TPQA036 Version 2)

Sponsor:	AstraZeneca AB	Protocol/CIP Number:	D7550C00003
CIL Project Number:	40343		

All these secondary variables will be also listed for Efficacy Analysis Set at each visit.

8.6.3 Analysis of Pharmacokinetic Variables

The analysis will be based on the PK analysis set.

Summary statistics will be provided for plasma concentrations of AZD5718 according to the protocol scheduled time. Plasma concentrations will also be displayed overtime by subject. The number of samples below the limit of quantification will be also be summarized.

8.6.4 Subgroup Analyses

Not applicable.

8.7 Analysis of exploratory parameters and cardiovascular biomarkers

The exploratory parameters are:

- Carotid-femoral pulse wave velocity and brachial pulse wave analysis (cfPWV/bPWA):
 - Augmentation index,
 - Carotid-femoral pulse wave velocity,
 - Pulse pressure amplification,
 - Central pulse pressure,
 - Central blood pressure systolic/diastolic,
 - Brachial blood pressure systolic/diastolic
- Clinical Outcome Assessments:
 - SF-36 (physical component summary (PCS), mental component summary (MCS), perceived change in health and each of the 8 health domain scores)
 - EQ-5D overall score
 - Rose Dyspnoea overall score
 - FACIT-Fatigue Prorated score
- GRACE 2.0 score at baseline
- Exploratory cardiovascular biomarker:
 - Total cholesterol
 - Low density lipoprotein cholesterol (LDL-C)
 - High density lipoprotein cholesterol, (HDL-C)
 - Triglycerides
 - hsTnI (high sensitive Troponin I)
 - hsCRP (High-sensitivity C-Reactive Protein)
 - NT-proBNP (N-Terminal Prohormone of Brain Natriuretic Peptide)
 - Lp(a)* (Lipoprotein a)
 - ApoA1* (Apolipoprotein A)
 - ApoB*

Distribution:

Original:

Copy:

TPCA025 Version 2 (based on TPQA036 Version 2) Effective Date: 27th August 2017 Prior Effective Date: 21st December 2016

Sponsor:	AstraZeneca AB	Protocol/CIP Number:	D7550C00003
CIL Project Number:	40343		

The exploratory endpoints related to all the exploratory variables (except GRACE score) are the changes from baseline, at Visit 4 and Visit 4c. The exploratory endpoint for GRACE 2.0 score is based only on the value at baseline.

Detailed description of the statistical analyses for each of these variables is reported in the following sections.

8.7.1 Carotid-femoral pulse wave velocity and brachial pulse wave analysis

cfPWV/bPWA variables will be analysed based on the Efficacy Analysis Set. For the cfPWV/bPWA variables assessment please refer to section 6.9.1.

These variables will be firstly tested for Normality (Normality will be evaluated using Q-Q plots) Then the changes at visit 4 and the changes at visit 4c will be analysed using the MMRM model described in section 7.1 using data from visit 2, 4 and 4c.

If the distribution appears to be Normal, the analysed change will be the Visit value minus the Baseline value. The reportable results will be those for Normal variables.

If the distribution appears to be log-Normal, the analysed change will be the Visit value in log minus the Baseline value in log. The reportable results will be those for log-Normal variables.

Two-sided test will be used to compare the change from baseline observed in the active group vs the change from baseline observed in the placebo group. Alpha level will be set at 0.05.

Comparison of AZD5718 versus placebo will also be assessed within the same model.

For further details on the model please refer to Appendix 2 and to the table in Appendix 3.

In addition to the results above, also descriptive statistics by group for all visits, for the actual value and for the change from baseline will be reported. Change from baseline is calculated as Visit value minus Baseline value.

cfPWV/bPWA variables will be also listed for Efficacy Analysis Set at each visit.

8.7.2 Clinical Outcome Assessments

PRO questionnaires will be analysed based on the Efficacy Analysis Set using data from Visits 2, 4 and 4c. For the PRO questionnaires assessment please refer to section 6.9.2.

The changes at visit 4 and the changes on visits 4c on PRO questionnaires will be analysed using the MMRM described in section 7.1 using data from visit 2, 4 and 4c.

Distribution:

Original:

Copy:

TPCA025 Version 2 (based on TPQA036 Version 2)

Sponsor:	AstraZeneca AB	Protocol/CIP Number:	D7550C00003
CIL Project Number:	40343		

PRO questionnaires are normal distributed variables. The analysed change will be the Visit value minus the Baseline value.

Two-sided test will be used to compare the change from baseline observed in the treated group vs the change from baseline observed in the placebo group. Alpha level will be set at 0.05. The reportable results will be those for Normal variables.

Comparison of AZD5718 versus placebo will also be assessed within the same model.

For further details on the model please refer to Appendix 2 and to the table in Appendix 3.

In addition to the results above, also descriptive statistics by group for all visits, for the actual value and for the change from baseline will be reported. Change from baseline is calculated as Visit value minus Baseline value.

PRO questionnaires scores will be also listed for Efficacy Analysis Set at each visit.

8.7.3 GRACE 2.0 score at baseline

GRACE score at baseline will be summarized descriptively. The description will be performed based on the Efficacy Analysis Set.

GRACE score at baseline will be also listed for Efficacy Analysis Set at each visit.

8.7.4 Cardiovascular biomarkers

Cardiovascular biomarkers will be analysed based on the Efficacy Analysis Set. For additional details see section 6.8.

These variables will be firstly tested for Normality (Normality will be evaluated using Q-Q plots) and then changes at visit 4 and 4c analysed using the MMRM model described in section 7.1 using data from visit 2, 3, 4 and 4c.

If the distribution appears to be Normal, the analysed change will be the Visit value minus the Baseline value. The reportable results will be those for Normal variables.

If the distribution appears to be log-Normal, the analysed change will be the Visit value in log minus the Baseline value in log. The reportable results will be those for log-Normal variables.

Two-sided test will be used to compare the change from baseline observed in the active group vs the change from baseline observed in the placebo group. Alpha level will be set at 0.05.

Comparison of AZD5718 versus placebo will also be assessed within the same model.

For further details on the model please refer to Appendix 2 and to the table in Appendix 3.

Distribution:

Original:

Copy:

TPCA025 Version 2 (based on TPQA036 Version 2)

Sponsor:	AstraZeneca AB	Protocol/CIP Number:	D7550C00003
CIL Project Number:	40343		

In addition to the results above, also descriptive statistics by group for all visits, for the actual value and for the change from baseline will be reported. Change from baseline is calculated as Visit value minus Baseline value.

Cardiovascular parameters will be also listed for Efficacy Analysis Set at each visit.

8.8 Analysis of Safety

8.8.1 Extent of Exposure and Compliance to Study Treatment

Exposure and compliance are calculated as described in section 6.6.1.

Exposure

Exposure (days) and cumulative exposure over time (days) will be summarized by treatment group and by cohort of patients based on the Safety Analysis Set.

Exposure over time in terms of percentage of patients on treatment, will be also graphically shown by treatment group.

Exposure and actual exposure will be listed for Safety Analysis Set.

Compliance

Both, overall compliance and compliance categories will be summarized by treatment group and overall and by cohort of patients, based on the Safety Analysis Set.

Compliance will be listed for Safety Analysis Set.

8.8.2 Adverse Events

AEs will be assigned to the study phases as described in section 6.6.2.

Unless otherwise specified, AEs and SAEs will be summarized using the Safety Analysis Set by treatment group and by cohort of patients. Percentages will be based on the total numbers of subjects in the treatment group.

Subjects with multiple events in the same category will be counted only once in that category. Subjects with events in more than 1 category will be counted once in each of those categories. Unless otherwise specified On-treatment and Off-treatment phases will be reported separately for each summary table.

The following summary tables will be reported:

An overview table for all the AEs.

The number and percentage of subjects with the most common AEs (frequency>3%) for each Preferred Term (PT);

Distribution:

Original:

Copy:

TPCA025 Version 2 (based on TPQA036 Version 2) Effective Date: 27th August 2017 Prior Effective Date: 21st December 2016

Sponsor:	AstraZeneca AB	Protocol/CIP Number:	D7550C00003
CIL Project Number:	40343		

The number and percentage of subjects with any AEs for each System Organ Class (SOC) and PT;

The number and percentage of subjects with any AEs by maximum intensity for each PT;

The number and percentage of subjects with any AEs by investigator's causality assessment for each PT;

The number and percentage of subjects with AEs with outcome of death for each SOC and PT;

The number and percentage of subjects with AEs with outcome of death and with causality related to study drug for each SOC and PT in the On-treatment phase.

Key subject information for all subjects with AEs with outcome of death (On-treatment and Off-treatment phases together in the same table).

Time from first dose to AE (day) will be calculated as start date of the AE minus date of first dose +1. Time from last dose to death (day) will be calculated as death date minus date of last dose +1. Time from first dose to death (day) will be calculated as death date minus date of first dose +1. Durations will be calculated only for fully completed dates.

The number and percentage of subjects with death.

The number and percentage of subjects with any SAEs for each SOC and PT;

The number and percentage of subjects with any SAEs with causality related to study drug for each SOC and PT in the On-treatment phase.

Key subject information for all subjects with SAEs.

Time from start of treatment to onset of AE will be calculated as start date of the AE minus date of first dose +1.

Time from last dose prior to AE start date will be calculated only for AEs starting after the discontinuation of the study treatment. It will be calculated as start date of the AE minus date of last dose +1.

Time from start of treatment to becoming serious will be calculated as date in which the AE met criteria for serious AE minus date of first dose +1.

Durations will be calculated only for fully completed dates.

The number and percentage of subjects with AEs leading to treatment discontinuation for each SOC and PT in the On-treatment phase.

Distribution:

Original:

Copy:

TPCA025 Version 2 (based on TPQA036 Version 2)

Sponsor:	AstraZeneca AB	Protocol/CIP Number:	D7550C00003
CIL Project Number:	40343		

The number and percentage of subjects with AEs leading to treatment discontinuation and with causality related to study drug for each SOC and PT in the On-treatment phase.

Key subject information for all subjects with AEs leading to discontinuation.

Time from start of treatment to onset of AE will be calculated as start date of the AE minus date of first dose +1.

Time from start of treatment to discontinuation will be calculated as discontinuation date minus start of treatment date +1.

Durations will be calculated only for fully completed dates.

The number and percentage of subjects with AEs leading to treatment interruption for each SOC and PT in the On-treatment phase.

The number and percentage of subjects with any non-serious AEs only for those categories which show more that 5% of frequency, globally and for each PT. This table will be produced as a separate pdf output to meet clinical trial transparency requirements and not for inclusion in the CSR. It will be delivered at the same time as the CSR outputs.

Listings will also be presented by subject for all AEs using the Safety Analysis Set. Duration (day) will be calculated as stop date minus start date +1. Duration will be calculated only for complete dates. Listing of SAEs will also be presented for enrolled but not randomized subjects and for subjects who were not exposed to treatment.

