The total number of patients that will be randomized in the study has been increased from 100 to approximately 138. The reason for increasing the total number of patients is to make sure that there are enough patients to evaluate the sustained effect on CFVR after 12 weeks, that is, about 33 evaluable patients per arm for AZD5718 [REDACTED] and placebo. An evaluable patient is defined as a patient with a valid CFVR measurement at Visit 2 (baseline), and one postbaseline visit as judged by the CFVR Core lab. The total number of patients for evaluation of uLTE₄ and CFVR at week 4 will be more than 33 patients per high-dose and

placebo arm (exact number will be known at the unblinding at the end of the trial). This is due to the fact that patients that are already randomized to the study (approximately 38) will have a treatment period of 4 weeks while future randomized patients (approximately 100) will have a treatment period of 12 weeks.

Section 1.4 (Study Design) has been updated to reflect this change, however, the updated numbers are reflected in all relevant sections of the CSP.

Interim analysis

The interim analysis is updated as follows: The text is revised to alter the futility interim analysis to two administrative interim analyses for internal decision making. The futility analysis has been removed to be able to evaluate the sustained effect on u-LTE₄ at 12 weeks. The focus of the study extended to 12 weeks aiming on evaluation 5-LO pathway inhibition, ie not only at the end of 4 weeks but at the end of 12 weeks to ensure the use of the drug in a chronic setting. The futility analysis has therefore been changed into two administrative interim analyses for internal decision making. In the event of positive outcome at any of the administrative interim analyses an evaluation of exposure-response relationship may be performed. This is reflected in the Study Synopsis (Statistical methods) and Section 8.5.6 (Interim analysis).

Biomarker sampling

An additional biomarker sample will be collected at day 2 after the ACS.

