1.4 Study Design

This is a randomized, single-blind, placebo-controlled, parallel-group, multicentre study in subjects with CAD.

NB. The study was originally designed to be a 4-week study and was amended to be a 12-week study. As a consequence, some patients will have a treatment period of 4 weeks only while others will have a treatment period of 12 weeks. Visits 4b and 4c only apply to patients included under the amended CSP.

The study will be conducted at approximately 10 centres in 3 countries (Denmark, Finland and Sweden).

Patients suitable for the study will be identified and screened for eligibility after being hospitalized for ACS (Visit 1) comprising STEMI or NSTEMI. At Visit 1, after signing informed consent, biomarker sampling will take place at days 1, 2, 3 and 5 post ACS, where feasible. It is planned that approximately 138 CAD patients will be randomized to ensure at least 66 evaluable patients receiving AZD5718 [REDACTED] or placebo are included with 12 weeks treatment. An evaluable patient is defined as a patient with a valid CFVR measurement at Visit 2 (baseline) and one postbaseline visit as judged by the CFVR Core lab. For supporting dose selection in future studies, a treatment arm with 20% of randomized patients receiving AZD5718 [REDACTED] is included in the study.

On Day 1 (Visit 2), 7-28 days after the ACS event, patients willing to participate in the study will complete the screening procedure and, if eligible, be randomized in a ratio 2:1:2 to receive either AZD5718 (██████), AZD5718 (██████) or Placebo. Treatment duration will be 12 weeks, once daily administration in the morning. Dose on Visit 2 (Day 1), Visit 3 (2 weeks), Visit 4 (4 weeks), and Visit 4c (12 weeks) will be given by study personnel at the study site.

[figure not shown]
During the treatment phase, patients will come in to the clinic for study measurements at 2 weeks (Visit 3), 4 weeks (Visit 4), 8 weeks (Visit 4b) and 12 weeks (Visit 4c).

A follow-up visit (Visit 5) will be performed at 4 weeks (± 4 days) after last dose in order to ensure safety and well-being of the patients.

[figure not shown]
Study overview is presented in [Figure 1](#) below. For details and timings of the study assessments refer to [Table 1](#) Section 4.

Based on emerging data from the study AstraZeneca may decide to use the plasma/serum and/or urine samples collected in the study to address other study objectives than the pre-specified for a specific sample.

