7.9 Examination of Subgroups

Type of MI (STEMI or NSTEMI) is used as a stratification factor in the randomization and will be summarized using descriptive statistics.

Two cohorts of patients will be distinguished:

- Cohort 4w treatment: patients randomized before the CSP v3 implementation, who belong to 4 weeks of treatment
- Cohort 12w treatment: patients randomized after the CSP v3 implementation, who belong to 12 weeks of treatment

Distribution:

Original:

Copy:

TPCA025 Version 2 (based on TPQA036 Version 2)

Sponsor:	AstraZeneca AB	Protocol/CIP Number:	D7550C00003
CIL Project Number:	40343		

Unless otherwise specified, the statistical outputs will be presented jointly for the two cohorts.

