Table 14.3.2.15 - Adverse events with outcome of death, causally related to study treatment - Cohort 4 weeks treatment and Cohort 12 weeks treatment - On treatment (Safety Analysis Set) Table 14.3.2.16 - Adverse events with outcome of death - Cohort 4 weeks treatment and Cohort 12 weeks treatment - key subject information (Safety Analysis

Set)

Table FDAAA1-1 - Non-serious adverse events occurring in greater than 5% of subjects - Cohort 4 weeks treatment and Cohort 12 weeks treatment - On Trable FDAAA1-2 - Non-serious adverse events occurring in greater than 5% of subjects - Cohort 4 weeks treatment and Cohort 12 weeks treatment - Off

treatment (Safety Analysis Set)

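### Adverse event tables are split by 4-week and 12-week cohort, but the stated percentage denominator is the treatment group total, so the rule read literally misstates cohort rates

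*SAP*

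**What the plan says.** SAP 8.8.2 sets the layout of the safety tables: "AEs and SAEs will be summarized using the Safety Analysis Set by treatment group and by cohort of patients". The next sentence gives the denominator: "Percentages will be based on the total numbers of subjects in the treatment group". SAP 8.10.3 repeats both sentences for the interim analyses.

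Two other sections fix what the terms mean. SAP 7.1 describes the treatment groups as the two AZD5718 doses and placebo. SAP 7.9 defines the cohorts separately. The shorter-treatment cohort is given as "Cohort 4w treatment: patients randomized before the CSP v3 implementation, who belong to 4 weeks of treatment". The definition for those who entered under the extended schedule reads "Cohort 12w treatment: patients randomized after the CSP v3 implementation, who belong to 12 weeks of treatment".

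SAP 7.9 presents outputs for both cohorts jointly unless a section specifies otherwise, which 8.8.2 does. The table list in SAP section 12 carries the split into the output titles, for example "Non-serious adverse events occurring in greater than 5% of subjects - Cohort 4 weeks treatment and Cohort 12 weeks treatment". Tables 14.3.2.9 to 14.3.2.12 each cover one cohort alone.

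**The concern.** The layout has two dimensions, treatment and cohort, but the denominator rule names only treatment. A count from one cohort divided by a total that includes the other is not a rate in either cohort. The error would also be unequal: the smaller 4-week cohort would be understated much more than the 12-week cohort.

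The protocol (1.2 and 1.3) gives a fuller safety profile under longer exposure as a reason for extending treatment to 12 weeks. Readers will look across the cohort columns for signs that events accumulate with exposure. Under the literal rule, identical true rates would show a rise from 4 to 12 weeks that comes only from the denominator.

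**Working it through.** **Inputs**

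- Total: "It is planned that approximately 138 CAD patients will be randomized" (Protocol 1.4).
- 4-week cohort: "patients that are already randomized to the study (approximately 38) will have a treatment period of 4 weeks" (Protocol version history).
- 12-week cohort: "future randomized patients (approximately 100) will have a treatment period of 12 weeks" (same place; the synopsis also gives about 100).
- 12-week patients per arm: about 40, 20 and 40 (Protocol 8.2).
- Allocation 2:1:2 (SAP 4.3), assumed here to hold in both cohorts.

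**Reproducing the plan's counts.** For CFVR, the log difference is ln(1.2) = 0.182 and the SD is √ln(1 + 0.3²) = 0.294. A one-sided 5% test with 80% power needs 33 per arm, as stated (power 81.0% at 33). Dividing by 1 − 0.18 gives 33/0.82 = 40.2 and 17/0.82 = 20.7, against the stated 40 and 20. Then 40 + 20 + 40 = 100 and 138 − 100 = 38, so the cohort sizes agree with each other.

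**Expected numbers per arm**

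| Arm | 4-week | 12-week | Pooled |
|---|---|---|---|
| High dose, placebo (each) | 0.4 × 38 = 15.2 | 0.4 × 100 = 40 | 55.2 |
| Low dose | 0.2 × 38 = 7.6 | 0.2 × 100 = 20 | 27.6 |

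**Factor by which the literal rule divides a cohort rate** (pooled N / cohort N)

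- 4-week: 55.2/15.2 = 27.6/7.6 = 138/38 = 3.63
- 12-week: 55.2/40 = 27.6/20 = 138/100 = 1.38

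**Example.** A true rate of 20% in both cohorts prints as 20%/3.63 = 5.5% and 20%/1.38 = 14.5%. The apparent ratio between cohorts is 3.63/1.38 = 2.63, where the true ratio is 1.

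**Between arms, within the 4-week cohort.** Take true rates of 20% and 10%. They print as 5.5% and 10%/3.63 = 2.8%. The ratio stays at 2, but the difference shrinks from 10 points to 10/3.63 = 2.8 points.

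**Sensitivity of 3.6 (assumed ranges)**

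- A 4-week cohort of 30 to 46, plus 100: 130/30 = 4.3 to 146/46 = 3.2.
- 13 to 17 four-week patients in a main arm, plus 40: 53/13 = 4.1 to 57/17 = 3.4.
- 6 to 9 in the low-dose arm, plus 20: 26/6 = 4.3 to 29/9 = 3.2.

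**First interim analysis.** The trigger is at least 45 patients with a Visit 4 CFVR measurement (SAP 8.10). If, as an assumption, 38 of 45 were 4-week patients, the 4-week factor would be 45/38 = 1.2. The remaining 7 twelve-week patients would have a factor of 45/7 = 6.4, on counts too small to interpret. The final-analysis factors should therefore not be carried over to 8.10.3.

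**The case against.** The strongest reply is that this is loose wording and would not produce a wrong table. The denominator sentence comes straight after the words about cohorts, so a programmer may take treatment group to mean the treatment column within the cohort being shown. That is the natural build for Tables 14.3.2.9 to 14.3.2.12. The sentence also has another evident purpose: it replaces the SAP 7.1 default of using subjects with non-missing data, which does not suit adverse events. Section 12 lists only titles, so the column totals cannot be checked.

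Much of this stands. The in-cohort reading would remove the error and may well be what is intended. But the SAP nowhere states it, and its own description of treatment group points the other way.

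It is also fair that the tables print counts beside percentages, so a wrong denominator could be seen and corrected. The cohorts are sequential and not randomized against each other, and no formal comparison between them is planned. The AE table by system organ class and preferred term has no frequency threshold, and the listings are complete.

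A reader might go further and infer that events would drop out of the >5% non-serious table. For instance, 2 of 15 four-week patients (13.3%) would print as 2/55 = 3.6%. The documents do not support this as a finding. It requires the cut-off to be applied to cohort percentages, and SAP 8.8.2 does not say that. If the cut-off is applied to the pooled arm, a pooled denominator is correct. What remains is that the SAP does not say which denominator the cut-offs use.

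**Conclusion.** The concern holds as a defect in the written rule. Followed literally at the final analysis, it would divide 4-week cohort percentages by about 3.6 and 12-week percentages by about 1.4, and would create a difference between cohorts where none exists. Absolute rates and risk differences would be distorted. Between-arm ratios within a cohort would be about unchanged, provided the cohort split is similar across arms. No efficacy test or estimate is affected.

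These sizes rest on the approximate 38/100 split, on 2:1:2 allocation in both cohorts, and on the literal reading. The 3.6 is an expected value and not a ceiling. It also belongs to the 4-week cohort only, so it should not be read as the understatement of the 12-week safety profile, where the factor is 1.38. At the first interim analysis the 4-week factor would be different and smaller.

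This is a reporting clarification worth making before the tables are programmed. It does not show that rates will in fact be misreported.

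**What to change.** In SAP 8.8.2 and 8.10.3, replace the denominator sentence with: *Percentages in cohort columns or cohort tables will be based on the number of Safety Analysis Set subjects in that treatment group and cohort; pooled columns use the treatment group total.*

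In the same sections, state whether the >3% cut-off (common events, 8.8.2) and the >5% cut-off (non-serious events, both sections) are applied to cohort or pooled percentages, and use the matching denominator.

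The cost is a short text change in two places. It needs no new data and changes nothing in trial conduct, the efficacy analyses or the type I error.
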